1. PROTOCOL SUMMARY

1.1. Synopsis

Protocol Title: A Multi-Center, Open-Label Trial to Evaluate the Pharmacokinetics, Safety, and Pharmacodynamics of Subcutaneously Administered Belimumab, a Human Monoclonal Anti-BLyS Antibody, Plus Standard Therapy in Pediatric Participants with Systemic Lupus Erythematosus (SLE)

Short Title: Open label Study of Subcutaneous Belimumab in Pediatric Participants with Systemic Lupus Erythematosus (SLE)

Rationale: The purpose of this study is to evaluate the pharmacokinetics (PK), safety, and pharmacodynamics (PD) of repeat doses of 200 mg belimumab administered subcutaneously (SC) in pediatric participants 5 to 17 years of age with systemic lupus erythematosus (SLE) on a background of standard of care therapy. This bridging PK study is part of an extrapolation strategy to support the use of SC belimumab in pediatric SLE patients, based on the completed adult SLE study with SC belimumab and the pediatric SLE study with IV belimumab, and is a component of a post-approval commitment to EMA (EMA-000520-PIP02-13-M01) and FDA (postmarketing requirement 3239-1 under BLA 761043).

Objectives and Endpoints:

Objective	Endpoint
Primary - Pharmacokinetics	

 To characterize the PK profile of belimumab 200 mg SC in pediatric SLE participants. 	
 Observed belimumab concentrations at Week 12. Steady-state PK parameters: Cavg (AUC), Cmax, Cmin (based on population PK estimates).
Secondary - Safety	

 To evaluate the safety and tolerability of belimumab 200 mg SC in pediatric SLE participants. 	
 Incidence of adverse events, serious adverse events and adverse events of special interest through Week 52.
Secondary - Biomarkers	

 To characterize the pharmacodynamic profile of SC belimumab 200 mg SC in pediatric SLE participants. 	
 Change from baseline in biomarkers (C3/C4, anti-dsDNA, B cell subsets, and immunoglobulins) at Weeks 12 and 52.
Other - Efficacy	

 To characterize the impact on disease activity of belimumab 200 mg SC in pediatric SLE participants 	
 Percent of subjects with a ≥ 4 point reduction from baseline in SELENA SLEDAI at Weeks 12 and 52.

Overall Design:

This is a single arm, multi-center open-label study to evaluate the PK, safety, and PD of SC belimumab plus background standard therapy in approximately 28 pediatric participants ages 5 to 17 years of age and weighing ≥ 15 kg with active SLE. The study will include:

- Part A: Open-label, 12-week treatment phase.
- Part B: Optional 40-week open-label continuation phase for any participant who completes Part A.
- Post-treatment follow-up assessments at 8 and 16 weeks after the last dose of SC belimumab.
- Optional Access Extension Phase: Optional post-Week 52 extension phase exclusively for eligible participants who complete Part B (e.g., participants from countries where the IV formulation is not approved for pediatric use; or participants in whom IV Benlysta is not suitable due to medical reasons or significant logistical challenges).

Disclosure Statement: This is a single group, treatment study with one arm with no masking.

Number of Participants:

It is expected that 36 participants will need to be screened to enroll approximately 28 participants aiming to achieve 24 evaluable participants at Week 12. Enrollment and study withdrawals will be closely monitored and if there is an impact on continuation of participants in the study due to the Coronavirus SARS-CoV-2 (COVID-19) pandemic, more than 36 participants may be screened, and more than 28 may need to be enrolled, to ensure the ability to achieve the evaluable target at Week 12.

Intervention Groups and Duration:

The total maximum duration of study participation (Part A and Part B) for each participant is 73 weeks (screening: 5 weeks, treatment: up to 52 weeks [12 weeks Part A plus 40 weeks extension phase] and follow-up: 16 weeks).

Cohort 1 will include participants ≥ 50 kg body weight, Cohort 2 will include participants ≥ 30 to < 50 kg body weight and Cohort 3 will include participants < 30 kg body weight at baseline. In Part A Cohort 1 will receive weekly doses of belimumab 200 mg SC, Cohort 2 will receive belimumab 200 mg SC every 10 days and Cohort 3 will receive belimumab 200 mg SC every 2 weeks.

In Part B, the dosing frequency may change according to pre-defined criteria based on changes in body weight of the participant.

The optional access extension phase is to provide a mechanism for continued access to belimumab SC from Week 52 onwards and is exclusive only for eligible participants who complete Part B of the study (e.g., participants from countries where the IV formulation

is not approved for pediatric use; or participants in whom IV Benlysta is not suitable due to medical reasons or significant logistical challenges for full eligibility criteria). The duration of this optional access extension phase will depend on age of the participants and the conditions for eligibility. During the access extension phase, the dosing frequency may change based on changes in body weight of the participant. Participants who are enrolled into the optional access extension phase will be withdrawn from treatment if they reach the age of 18 years, if Belimumab SC or IV becomes licensed and commercially available for pediatric use in the participant's country.

[figure not shown]
Safety Review Team (SRT)

An internal GSK Safety Review Team will monitor and perform in-stream review of safety data throughout Part A and Part B of the study. The optional access extension phase will not be part of this in-stream review.

Pharmacokinetic Review Team (PRT)

An internal GSK Pharmacokinetic Review Team will review in-stream PK data during Part A and Part B and if necessary recommend dose adjustments.

1.2. Schema

1.3. Schedule of Activities (SoA)

1.3.1. SOA 1. Part A - Cohort 1 (body weight ≥ 50 kg at baseline) and Cohort 3 (body weight < 30 kg at baseline)

Note: In Part B and in the optional accesss extension phase, participants may need to switch dosing frequency according to changes in body weight (See Section 6.6 Dose Modification)

Procedure	Part A - Subcutaneous PK/PD Safety [Cohort 1 and Cohort 3] Screening to Day 85 (Week -5 to 12)							Follow-Up Period ^{1,2}	
	Screening and eligibility -35 days ¹⁰	Treatment Period							
Study Day		Day 1	Day 8 ± 2 days	Day 15 ± 2 days	Day 29 ± 2 days	Day 57 ± 2 days	Day 85 ± 2 days	8-Week Follow-up ± 7 days ¹	16-Week Follow-up ± 7 days ^{1,2}
Study Week		Wk 0	Wk 1	Wk 2	Wk 4	Wk 8	Wk 12/EW ¹		
Written Informed Consent	X								
Demography	X								
Medical History	X								
Inclusion/Exclusion Criteria	X	X							
SELENA SLEDAl	X	X					X		
Vital Signs	X	X	X	X	X	X	X	X	
Weight + Height	X	X	X	X	X	X	X	X	
12-Lead ECG	X								
Physical Examination ³	X	X	X	X	X	X	X	X	

Procedure	Part A - Subcutaneous PK/PD Safety [Cohort 1 and Cohort 3] Screening to Day 85 (Week -5 to 12)							
	Screening and eligibility -35 days ¹⁰	Treatment Period						Follow-Up Period ^{1,2}
Study Day		Day 1	Day 8 ±2 days	Day 15 ±2 days	Day 29 ±2 days	Day 57 ±2 days	Day 85 ±2 days	8-Week Follow-up ±7 days ¹
Study Week	Wk 0	Wk 1	Wk 2	Wk 4	Wk 8	Wk 12/EW ¹		
Adverse Events ⁴	X	X	X	X	X	X	X	X
Concomitant Medications	X	X	X	X	X	X	X	X
Device incidents/malfunctions		X	X	X	X	X		
Laboratory Assessments								
Hematology	X	X			X	X	X	X
Urinalysis	X	X			X	X	X	X
Chemistry	X	X			X	X	X	X
Spot Urine (protein:creatinine)	X	X			X	X	X	X
Pregnancy Test ⁵	X	X	X	X	X	X	X	X
BLyS Protein ⁸		X						
PT/PTT	X							
C3/C4, CRP ⁸	X	X			X	X	X	X

Procedure	Part A - Subcutaneous PK/PD Safety [Cohort 1 and Cohort 3] Screening to Day 85 (Week -5 to 12)							
	Screening and eligibility -35 days ¹⁰	Treatment Period					Follow-Up Period ^{1,2}	
Study Day		Day 1	Day 8 ±2 days	Day 15 ±2 days	Day 29 ±2 days	Day 57 ±2 days	Day 85 ±2 days	8-Week Follow-up ±7 days ¹
Study Week		Wk 0	Wk 1	Wk 2	Wk 4	Wk 8	Wk 12/EW ¹	16-Week Follow-up ±7 days ^{1,2}
B-Cells ⁸		X		X	X	X	X	X
Anti-dsDNA, ANA ⁸	X	X			X	X	X	X
Immunogenicity		X			X		X	X
IgA, IgG and IgM ⁸	X	X			X	X	X	X
Hepatitis B, Hepatitis C, HIV	X							
Belimumab Administration and PK Sampling								
Training - Use of Autoinjector	X	X						
In Clinic Administration of Belimumab (Cohort 1 ≥50 kg) ⁶		X	X	X	X	X	X ⁹	
In Clinic Administration of Belimumab (Cohort 3 <30 kg) ⁷		X		X	X	X	X ⁹	
PK Sampling ⁸			X	X	X	X	X	X

1. 8- and 16-week follow-up is required for participants who withdraw from study treatment prior to the end of Part A and for participants who complete Part A but do not wish to continue into Part B. For participants who withdraw from treatment prior to Week 12, in addition to the 8- and 16-week follow-up visit and assessments, an early withdrawal visit (EW) should be completed. The EW visit requires identical assessments and procedures to the Week 12 visit.
2. 16-week follow-up requires a phone call to collect AEs, concomitant medications and the results of home urine pregnancy test (if applicable) for female participants. NOTE: the 16-week follow-up may be performed at a clinic visit per local requirement.
3. Full Physical Examination is required at screening (Section 8.1). An abbreviated/symptom-driven exam can be done thereafter.
4. Please refer to Section 8.9.1. for the time period for collection of AEs/SAEs
5. Serum pregnancy test required at screening for all females of childbearing potential. Urine pregnancy test is sufficient for all subsequent visits. A home pregnancy test (urine) will be provided to participants for the 16-week follow-up pregnancy assessment.
6. Cohort 1 (≥ 50 kg at baseline): Study drug to be administered weekly in Part A. Administration in clinic is mandated where specified in the Schedule of Activities (SOA), otherwise at home self-administration is encouraged (see Section 6.4). For the first 2 doses (Day 1 and Week 0) participants must be observed for 3h post belimumab injection (see Section 6.4).
7. Cohort 3 (< 30 kg at baseline): Study drug to be administered every 2 weeks in Part A. Administration in clinic is mandated where specified in the SOA, otherwise at home self-administration is encouraged (see Section 6.4). For the first 2 doses (Day 1 and Week 1), participants must be observed for 3h post belimumab injection (see Section 6.4).
8. Samples must be taken pre-dose.
9. Dosing only occurs for participants who elect to continue in Part B.
10. Participants in Cohort 3 (< 30 kg) will have the screening blood collection and testing split across 2 visits separated by at least 2 weeks and between the 2nd screening and Day 1 visits to ensure the blood volume collected remains within local guidelines. Note: This may also apply to participants ≥ 30 kg according to local guidelines.

1.3.2. SOA 2 Part A Cohort 2 (Body weight ≥ 30 kg - < 50 kg at baseline)

Note: In Part B and in the optional access extension phase, participants may need to switch dosing frequency according to changes in body weight (See Section 6.6 Dose Modification)

Procedure	Part A - Subcutaneous PK/PD Safety [Cohort 2] Screening to Day 81 (Week -5 to 11 ⁹)							
	Screening and eligibility -35 days ¹⁰	Treatment Period					Follow-Up Period ^{1,2}	
Study Day		Day 1	Day 11 ± 2 days	Day 21 ± 2 days	Day 31 ± 2 days	Day 61 ± 2 days	Day 81 ¹ ± 2 days	8-Week Follow-up ± 7 days ¹
Written Informed Consent	X							
Demography	X							
Medical History	X							
Inclusion/Exclusion Criteria	X	X						
SELENA SLEDAl	X	X					X	
Vital Signs	X	X	X	X	X	X	X	
Weight + Height	X	X	X	X	X	X	X	
12-Lead ECG	X							
Physical Examination ³	X	X	X	X	X	X	X	
Adverse Events ⁴	X	X	X	X	X	X	X	X
Concomitant Medications	X	X	X	X	X	X	X	X

Procedure	Part A - Subcutaneous PK/PD Safety [Cohort 2] Screening to Day 81 (Week -5 to 11 ⁹)							
	Screening and eligibility -35 days ¹⁰	Treatment Period					Follow-Up Period ^{1,2}	
Study Day		Day 1	Day 11 ±2 days	Day 21 ±2 days	Day 31 ±2 days	Day 61 ±2 days	Day 81 ¹ ±2 days	8-Week Follow-up ±7 days ¹
Device incidents/malfunctions		X	X	X	X	X	X	
Laboratory Assessment								
Hematology	X	X			X	X	X	X
Urinalysis	X	X			X	X	X	X
Chemistry	X	X			X	X	X	X
Spot Urine (protein:creatinine)	X	X			X	X	X	X
Pregnancy Test ⁵	X	X	X	X	X	X	X	X
BLyS Protein ⁸		X						
PT/PTT	X							
C3/C4, CRP ⁸	X	X			X	X	X	X
B-Cells ⁸		X		X	X	X	X	X
Anti-dsDNA, ANA ⁸	X	X			X	X	X	X
Immunogenicity		X			X		X	X

Procedure	Part A - Subcutaneous PK/PD Safety [Cohort 2] Screening to Day 81 (Week -5 to 11 ⁹)								
	Screening and eligibility -35 days ¹⁰	Treatment Period						Follow-Up Period ^{1,2}	
Study Day		Day 1	Day 11 ±2 days	Day 21 ±2 days	Day 31 ±2 days	Day 61 ±2 days	Day 81 ¹ ±2 days	8-Week Follow-up ±7 days ¹	16-Week Follow-up ±7 days ^{1,2}
IgA, IgG and IgM ⁸	X	X			X	X	X	X	
Hepatitis B, Hepatitis C, HIV	X								
Belimumab Administration and PK Sampling									
Training - Use of Autoinjector	X	X							
In Clinic Administration of Belimumab (Cohort 2 ≥30 - <50kg) ⁶		X	X	X	X	X	X ⁷		
PK Sampling ⁸			X	X	X	X	X	X	

1. 8- and 16-week follow-up is required for participants who withdraw from study treatment prior to the end of Part A and for participants who complete Part A but do not wish to continue into Part B. For participants who withdraw from treatment prior to Day 81 (Week 11), in addition to the 8- and 16-week follow-up visit and assessments, an early withdrawal visit (EW) should be completed. The EW visit requires identical assessments and procedures to the Day 81 visit.
2. 16-week follow-up requires a phone call to collect AEs, concomitant medications and the results of home urine pregnancy test (if applicable) for female participants. NOTE – the 16-week follow-up may be performed at a clinic visit per local requirement.
3. Full Physical Examination is required at screening. An abbreviated/symptom-driven exam can be done thereafter as described in Section 8.8.1
4. Adverse Event collection: Please refer to Section 8.9.1
5. Serum pregnancy test required at screening for all females of childbearing potential. Urine pregnancy test is sufficient for all subsequent visits. A home pregnancy test (urine) will be provided to participants for the 16-week follow-up pregnancy assessment.
6. Cohort 2 (≥30 - <50 kg): Study drug to be administered every 10 days in Part A (see Section 6.4). Administration in clinic is mandated where specified in the Schedule of Activities (SOA), otherwise at home self-administration is encouraged (see Section 6.4). For the first 2 doses (Day 1 and Day 11) participants must be observed for 3h post belimumab injection (see Section 6.4). Note the visit schedule for Cohort 2 participants differs from Cohorts 1 and 3 but aligns with dosing schedule without adding additional visits.
7. Dosing occurs only for participants who elect to continue in Part B.
8. Samples must be taken pre-dose where the dose is administered on a clinic visit day.

9. Note – Study weeks are not shown for Cohort 2 as the weeks for this cohort do not align with those for Cohorts 1 and 3 for all visits. The visits for Cohort 2 should be planned according to the Study Days shown in the header.
10. Participants in Cohort 2 (≥ 30 - <50 kg) may have the screening blood collection and testing split across 2 visits separated by at least 2 weeks and between the 2nd screening and Day 1 visits to ensure the blood volume collected remains within local guidelines.

1.3.3. SOA 3 Part B - Applies to all participants who enter Part B

Note: Participants may need to switch dosing frequency according to change in body weight (See Section 6.6 Dose Modification)

Procedure	Part B - Optional Treatment Extension - Days 86-365 (Weeks 13-52) [All participants]								
	Treatment Period							Follow-Up Period	
Study Day	Day 113 ±7 days	Day 141 ±7 days	Day 169 ±7 days	Day 211 ±7 days	Day 253 ±7 days	Day 309 ±7 days	Day 365 ±7 days	8-Week Follow-up ±7 days ¹	16-Week Follow-up ±7 days ^{1,2}
Study Week	Wk 16	Wk 20	Wk 24	Wk 30	Wk 36	Wk 44	Wk 52/EW ¹	Wk 60	Wk 68 ²
SELENA SLEDAI							X		
Vital Signs	X	X	X	X	X	X	X	X	
Weight +Height	X	X	X	X	X	X	X	X	
Symptom Driven Physical Exam ³	X	X	X	X	X	X	X	X	
Adverse Events ⁴	X	X	X	X	X	X	X	X	X
Concomitant Medications	X	X	X	X	X	X	X	X	X
Collection of device events/malfunctions	X	X	X	X	X	X	X		
Laboratory Assessments									
Hematology	X	X	X	X	X	X	X	X	

Procedure	Part B - Optional Treatment Extension - Days 86-365 (Weeks 13-52) [All participants]								
	Treatment Period							Follow-Up Period	
Study Day	Day 113 ±7 days	Day 141 ±7 days	Day 169 ±7 days	Day 211 ±7 days	Day 253 ±7 days	Day 309 ±7 days	Day 365 ±7 days	8-Week Follow-up ±7 days ¹	16-Week Follow-up ±7 days ^{1,2}
Study Week	Wk 16	Wk 20	Wk 24	Wk 30	Wk 36	Wk 44	Wk 52/EW ¹	Wk 60	Wk 68 ²
Urinalysis	X	X	X	X	X	X	X	X	
Chemistry	X	X	X	X	X	X	X	X	
Spot Urine (protein to creatinine ratio)	X	X	X	X	X	X	X	X	
Pregnancy Test ⁵	X	X	X	X	X	X	X	X	X
C3/C4, CRP ¹⁰			X				X	X	
B-Cells ¹⁰			X				X	X	
Anti-dsDNA and ANA ¹⁰			X				X	X	
Immunogenicity			X				X	X	
IgA, IgG and IgM ¹⁰	X	X	X	X	X	X	X	X	
Belimumab Administration and PK Sampling									
Cohort 1 Administration of Belimumab (Body weight \geq 50 kg) ^{6,9}	Once weekly (\pm 2 days) until Week 51 (inclusive)								

Procedure	Part B - Optional Treatment Extension - Days 86-365 (Weeks 13-52) [All participants]								
	Treatment Period							Follow-Up Period	
Study Day	Day 113 ±7 days	Day 141 ±7 days	Day 169 ±7 days	Day 211 ±7 days	Day 253 ±7 days	Day 309 ±7 days	Day 365 ±7 days	8-Week Follow-up ±7 days ¹	16-Week Follow-up ±7 days ^{1,2}
Study Week	Wk 16	Wk 20	Wk 24	Wk 30	Wk 36	Wk 44	Wk 52/EW ¹	Wk 60	Wk 68 ²
Cohort 2 Administration of Belimumab (Body weight \geq 30 kg to <50kg) ^{7,9}	Every 10 days(± 2 days) until Day 361 (inclusive)								
Cohort 3 Administration of Belimumab (Body weight <30kg) ^{8,9}	Every 2 weeks (±2 days) until Week 50 (inclusive)								
PK Sampling ¹⁰	X		X		X		X	X	

1. If participants withdraw from treatment prior to Week 52, in addition to the 8- and 16-week follow-up visit and assessments, an early withdrawal (EW) visit should, if possible, be completed. The EW visit requires identical assessments and procedures to the Week 52 visit. The 8- and 16-week follow-up visits are **NOT** required for participants who are eligible for and are enrolled into the optional access extension phase.
2. 16-week follow-up requires a phone call to collect AEs, concomitant medications and report results of home urine pregnancy test (if applicable) for female participants. NOTE – the 16-week follow-up may be performed at a clinic visit per local requirement.
3. An abbreviated/symptom-driven exam can be done as described in Section 8.8.1
4. Please refer to Section 8.9.1 for the time period for collection of AEs/SAEs.
5. Urine pregnancy test is sufficient for all visits in Part B. A home pregnancy test (urine) will be provided to participants for the 16-week follow-up pregnancy assessment.
6. Cohort 1 (\geq 50 kg at baseline): Study drug to be administered weekly. Wherever the dosing days coincide with clinic visits IP administration in clinic is mandated. PK and/or biomarker sample collection, where specified, must be pre-dose at these visits.
7. Cohort 2 (\geq 30 kg - <50 kg at baseline): Study drug to be administered every 10 days. Wherever the dosing days coincide with clinic visits IP administration in clinic is mandated. PK and/or biomarker sample collection, where specified, must be pre-dose at these visits.
8. Cohort 3 (15 - <30 kg at baseline): Study drug to be administered every 2 weeks. Wherever the dosing days coincide with clinic visits IP administration in clinic is mandated. PK and/or sample collection, where specified, must be pre-dose at these visits.

9. In Part B the dosing frequency may be switched according to any change in body weight. Please refer to Section [6.6](#) Dose Modification. IF a participant switches dosing frequency due to weight changes during Part B, the last IP administration will be according to the schedule provided at Week44. Individual cases will be consulted with and resolved by the Medical Monitor.
10. Samples must be taken pre-dose where the dose is administered on a clinic visit day.

1.3.4. SOA 4 Optional Access Extension Phase - Applies exclusively to eligible participants who complete Part B

Note: Participants may need to switch dosing frequency according to changes in body weight (See Section 6.6 Dose Modification)

Procedure	Optional Access Extension phase - From Week52 [Eligible participants only]				
	Treatment Period			Follow-Up Period ^{1,2}	
Study Day	Day 365 ±7 days	Visit Every 12 Weeks until the end of Access Extension ±7 days ¹	End of access extension /EW ¹	8-Week Follow-up ±7 days ^{1,2}	16-Week Follow-up ±7 days ^{1,2}
Study Week	Wk 52				
Access Extension Phase Specific Eligibility Criteria	X				
Access Extension Phase -Specific Written Informed Consent	X				
Weight ³	X	X			
Serious Adverse Events ⁴	X	X	X	X	X
Collection of device events/malfunctions	X	X	X	X	
Laboratory Assessments					
Pregnancy Test ⁵	X	X	X	X	X
Belimumab Administration					
Administration of Belimumab (Body weight ≥50 kg) ^{6,9}	X	X			
Administration of Belimumab (Body weight ≥30 kg to <50kg) ^{7,9}	X	X			

Procedure	Optional Access Extension phase - From Week52 [Eligible participants only]				
	Treatment Period			Follow-Up Period ^{1,2}	
Study Day	Day 365 ±7 days	Visit Every 12 Weeks until the end of Access Extension ±7 days ¹	End of access extension /EW ¹	8-Week Follow-up ±7 days ^{1,2}	16-Week Follow-up ±7 days ^{1,2}
Study Week	Wk 52				
Administration of Belimumab (Body weight <30kg) ^{8,9}	X	X			

1. If participants withdraw from treatment at anytime during the optional access extension phase, in addition to the 8- and 16-week follow-up visits, an early withdrawal (EW) visit should, if possible, be completed.
2. 8 and 16-week follow-up requires a phone call to collect SAEs, and the results of home urine pregnancy test (if applicable) for female participants. NOTE: the 8-Week and 16-week follow-up may be performed at a clinic visit per local requirement.
3. Any changes in body weight that lead to a change in dosing frequency should be noted and requested in the IWRS system as per Section 6.7.1.5 (see SRM for details).
4. Please refer to Section 6.7.1.5 for SAE reporting in the optional access extension phase and Section 8.9.1 for the time period for collection of SAEs.
5. For females of childbearing potential: urine pregnancy tests will be provided by sites. Participants will be required to perform a urine pregnancy test every 4 weeks throughout the treatment period (1 onsite and 2 at home). Home urine pregnancy tests will also be provided for the 8-week and 16-week follow-up period. The results of urine pregnancy tests conducted at home will be recorded in the subject diary cards and stored as part of the investigator's source documents. Only positive pregnancy test results will be reported to GSK during the optional access extension phase and will follow the guidance in Section 8.9.5.
6. Participants ≥50 kg at the start of the access extension phase: Study drug to be administered weekly. At home self-administration is encouraged.
7. Participants ≥30 kg - <50 kg at the start of the access extension phase: Study drug to be administered every 10 days. At home self-administration is encouraged.
8. Participants <30 kg at start of the access extension phase: Study drug to be administered every 2 weeks. At home self-administration is encouraged.
9. In the optional access extension phase the dosing frequency may be switched according to any change in body weight. Please refer to Section 6.6 Dose Modification.

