6.4. Subcutaneous Administration of Belimumab

“Self-administration” is defined as administration of study drug either by the study participant or by the participant’s parent/caregiver. All participants less than 12 years old must have the study drug administered by their parent/caregiver. Whether the study drug is administered by the participant for those 12 years and older will be determined by the participant and his/her parents/caregivers.

During screening and on Day 1 (prior to the participant receiving their first dose), qualified study site personnel must review study drug handling and administration techniques with the participant and their caregiver(s). After the first injection of belimumab on Day 1, all subsequent injections should be administered according to the schedule shown in the SOA Section 1.3 ±2 days. Please refer to Section 6.4.2 for guidance regarding missed doses.

If possible, the participant or their caregiver will administer the study agent by SC injection even if administered at the clinic visit. The first three doses will be administered under observation in the clinic. In the post-marketing setting with IV belimumab, delayed onset of symptoms of acute hypersensitivity reactions have been observed. Therefore, at each of the first 2 scheduled administrations of belimumab, participants will be observed by qualified site staff during dosing and will remain under observation at the clinic for 3 hours post-dose. Should symptoms of acute hypersensitivity occur, an extended period of monitoring may be appropriate, based on clinical judgement. Participants and caregivers should be made aware of the potential risk, the signs and symptoms of such reactions, and the importance of immediately seeking medical attention.

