5.8. Presentation of data

Continuous variables will be summarized using descriptive statistics (number of subjects, mean, standard deviation (SD), median, 25th percentile, 75th percentile, minimum and maximum).

Categorical variables will be summarized using counts and percentages.

Subjects are recruited into the study in different weight cohorts, with different planned visit dates during Part A (as per Protocol Section 1.3). The majority of the SAC outputs will present all of the data together, regardless of cohort. Table 4 shows the visits for Part A that are combined across the cohorts when outputs are presented by visit.

Table 4 Part A presentation of results by visit

	Target Study Day ¹		
Visit label on outputs	Cohorts 1 and 3	Cohort 2	
Week 1 (Day 8/11)	Day 8	Day 11	
Week 2 (Day 15/21)	Day 15	Day 21	
Week 4 (Day 29/31)	Day 29	Day 31	
Week 8 (Day 57/61)	Day 57	Day 61	
Week 12 (Day 85/81)	Day 85	Day 81	

¹ Target Study Day, relative to Baseline/Treatment Start Date as Day 1.

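### In SOA 1 the visit labels for the 3-hour post-dose observation do not match the first two doses in Cohorts 1 and 3

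*Protocol*

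**What the plan says.** SOA 1 covers Part A for Cohort 1 (50 kg or more) and Cohort 3 (under 30 kg). Footnote 6 gives the Cohort 1 interval, "Study drug to be administered weekly in Part A", and then the observation instruction: "For the first 2 doses (Day 1 and Week 0) participants must be observed for 3h post belimumab injection". Footnote 7 does the same for Cohort 3: "Study drug to be administered every 2 weeks in Part A", followed by "For the first 2 doses (Day 1 and Week 1), participants must be observed for 3h post belimumab injection". Both footnotes refer the reader to Section 6.4.

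Section 6.4 counts doses and names no visit: "at each of the first 2 scheduled administrations of belimumab, participants will be observed by qualified site staff during dosing", with a 3-hour stay in the clinic afterwards. Section 4.1 and the risk table in Section 2.3.1 state the same requirement, again by dose number. Sections 4.1 and 6.4 also have the first three doses given in the clinic under observation.

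The corresponding footnote for Cohort 2, in SOA 2, names Day 1 and Day 11.

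**The concern.** The risk table in Section 2.3.1 says that systemic and hypersensitivity reactions are more frequent with the first two doses and can be severe or fatal. Three hours of supervision after each of those doses is among its listed mitigations. Section 6.4 adds the reason for a prolonged stay: delayed onset of acute hypersensitivity, seen after marketing with the IV form.

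For Cohorts 1 and 3, SOA 1 is the only place that ties this requirement to calendar visits, and Section 8 makes adherence to the schedule mandatory. Sites commonly build visit checklists from such a table. If the label for the second dose is absent (Cohort 1) or points to a visit without an injection (Cohort 3), a checklist copied from it could leave the 3-hour stay off the visit where the second injection is given.

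The Cohort 3 slip is easy to overlook because those children do attend at Week 1, for PK sampling, vital signs and weight.

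**Working it through.** No sample size, power or error rate is involved. The check is a calendar comparison.

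**Inputs**
- Part A dosing intervals: 7 days (Cohort 1), 10 days (Cohort 2), 14 days (Cohort 3), from Section 4.1 and the SoA footnotes.
- Visit labels: the SOA 1 header puts Week 0 under Day 1, Week 1 under Day 8 and Week 2 under Day 15. SAP Section 5.8 (Table 4) and SAP Section 13.1.1 use the same correspondence for Cohorts 1 and 3.
- In-clinic dosing rows of SOA 1: Cohort 1 is marked at Days 1, 8, 15, 29, 57 and 85. Cohort 3 is marked at Days 1, 15, 29, 57 and 85, with the Day 8 cell empty.

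**Formulas**
- Week w falls on Day 7w + 1. Week 0 is Day 1, Week 1 is Day 8, Week 2 is Day 15.
- Dose k falls on Day 1 + (k − 1) × interval.

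| Cohort | Interval | Doses 1, 2, 3 | Footnote labels | Labels as days | Agreement |
|---|---|---|---|---|---|
| 1 | 7 days | Days 1, 8, 15 | Day 1 and Week 0 | Day 1 and Day 1 | Dose 1 named twice; no visit for dose 2 |
| 2 | 10 days | Days 1, 11, 21 | Day 1 and Day 11 | Day 1 and Day 11 | Both doses named |
| 3 | 14 days | Days 1, 15, 29 | Day 1 and Week 1 | Day 1 and Day 8 | Second label has no dose |

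**Could the visit windows explain Cohort 3?** No. With ±2 days, the Day 8 visit spans Days 6 to 10 and the Day 15 visit spans Days 13 to 17. The two do not overlap.

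**Could it be a table-reading fault?** No. Each footnote gives both the interval and the labels, and the intervals alone yield these dose days. The dosing rows agree with the intervals.

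**How the two errors differ.** Footnote 7 conflicts with its dosing row and with the interval stated in the same footnote. Footnote 6 does not conflict with its row, since Day 1 is a Cohort 1 dosing visit; it is incomplete, because it repeats the first visit.

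**Is the second injection still in the clinic?** Yes, in both cohorts. The rows mark Day 8 for Cohort 1 and Day 15 for Cohort 3, and the first three doses (Days 1, 8, 15 and Days 1, 15, 29) all fall on marked in-clinic days.

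**The case against.** The best defence is that only a parenthetical gloss is wrong. Both footnotes say that the instruction concerns the first two doses and send the reader to Section 6.4. Sections 2.3.1, 4.1 and 6.4 agree with one another, and nothing contradicts the dose count. A site that counts doses would observe the intended ones. The errors also tend to show themselves: a post-injection observation cannot be carried out at a visit without an injection, and two weekly doses cannot both fall on Day 1.

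Most of this stands, and it limits the weight of the point. It does not remove it. In-clinic dosing secures supervision of the injection but not the 3 hours afterwards, and those 3 hours are what the labels attach to a visit.

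Three stronger readings are tempting, and the documents do not support them:
- A reader might infer that the second injection could go unsupervised. The dosing rows and the rule for the first three doses exclude that.
- A reader might infer that every child in Cohorts 1 and 3 is affected, or the lightest children in particular. The footnotes change no dose, dosing day or clinic visit, and the heaviest cohort has the same kind of defect as the lightest.
- A reader might take footnote 7 to imply a Cohort 3 dose at Week 1. The interval in that footnote, the dosing row and the cohort table in Section 4.1 all speak against it.

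**Conclusion.** The inconsistency is certain; its consequence is only possible. In two of the three cohorts, one of the two labels in the observation footnote fails to identify the second dose: it duplicates the first visit in Cohort 1 and names a visit without a dose in Cohort 3. The exposure is one post-dose stay per child, and only where a site works from the labels rather than from the dose count. The number of children cannot be given, because the protocol plans about 28 participants in total without fixing the split by cohort.

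This is an inconsistency of text and not a fault of design. It touches no endpoint, analysis population, sample size or planned analysis; SAP Section 8.1.5.1 tabulates early reactions by injection and not by these labels. Nothing in the documents shows that an observation was missed.

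The conclusion assumes that the footnotes are meant to name the visits of the first two scheduled doses, as their wording and the Cohort 2 footnote indicate.

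**What to change.** Reconcile footnotes 6 and 7 of SOA 1 with the dosing rows of that table and with Sections 2.3.1, 4.1 and 6.4. The test for the corrected text should be that each footnote identifies the visits of that cohort's first and second scheduled doses. A looser test, that the named visits be dosing visits for the cohort, would leave footnote 6 unchanged, since Day 1 already meets it.

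The cost is two parentheses, changed by amendment or by a clarification letter to sites. If Part A dosing is already complete, the sponsor can instead check, where site records allow, whether the 3-hour stay after the second dose was kept in Cohorts 1 and 3. The review of protocol deviations before database lock (SAP Section 4.1) is a natural place for this.
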